To Compare Free Gingival Grafts and Connective Tissue Grafts Around Implants With Lack of Keratinized Mucosa

Study Protocol & Statistical Analysis Plan

NCT03338686

April 15, 2020

[name], MS, Principal Investigator
University of Alabama at Birmingham
Birmingham, AL 35294

A Prospective, Randomized Clinical Trial to Compare Free Gingival Graft and Connective Tissue Graft around Implants with a Lack of Keratinized Mucosa

Study Protocol

1. Objectives/Specific Aims:

The purpose of this study is to compare two commonly used soft tissue grafting techniques (FGG and CTG + gingivoplasty) to create/augment the soft tissue around dental implants with a lack of keratinized mucosa and to quantify the WKM gains at 6 and 12 months following incorporation at the recipient sites.

Secondary outcomes include evaluating the efficacy of gingivoplasty to induce keratinization, capturing changes in tissue thickness (tissue biotype), assessing esthetic outcomes using a newly developed peri-implant esthetic scale (PIES), and measuring patient-centered outcomes (pain, bleeding, swelling, patient satisfaction and change in daily activities) between the 2 groups. *Null hypothesis*: there will be a statistically significant difference between FGG and CTG + gingivoplasty when used to increase WKM around dental implants at 6 and 12 months post-op.

2. Materials and Method:

Study population

A total of 30 patients seeking treatment at the UAB SOD Graduate Periodontology clinics will be recruited to participate in this study according to the criteria in Table 1.

If deemed eligible, study visits, objectives, risks and benefits will be explained to all participants and IRB-approved written informed consent will be obtained. Conventional oral impressions will be made to fabricate a customized acrylic stent for reproducibility of clinical measurements. One trained calibrated examiner will be available for all study visits when clinical measurements are required. Photographs will be taken during all visits using a SLR digital camera in a 1:1 ratio.

Randomization

Randomization will take place on the day of surgery via sealed envelopes indicating the surgical approach the patient will receive, as follows:

Treatment Group 1: Free Gingival Graft (FGG)

Treatment Group 2: Connective Tissue Graft (CTG) + Laser Gingivolplasty (LG)

Table 1. Study Inclusion and Exclusion Criteria

Inclusion Criteria	Exclusion Criteria

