The non-inferiority design of the current study operates on an assumed standard deviation (SD) of .9 and a minimally clinically significant value (d) of 1 (1mm), based on previous studies of a similar nature. Based on these values, if there is truly no difference between the standard and experimental treatment, then N=26 patients are required to be 80% sure that the lower limit of a one-sided 97.5% confidence interval will be above the non-inferiority limit of –d.

Since the results will not follow a normal distribution, a Mann-Whitney U test will be used to compare the gains in KM around dental implants between the control (FGG) and test group (CTG+LP) at 6 months and 12 months post-operatively.

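### The 80% power at N=26 comes from a known-SD formula for means; a t-based interval gives 77.6%, and power for the named Mann-Whitney test was never computed

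*Combined protocol and SAP*

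**What the plan says.** The Statistical Analysis section sets a non-inferiority design. Its variability input is "an assumed standard deviation (SD) of .9". The margin d is 1 mm. The calculation supposes equal treatments, in the words "if there is truly no difference between the standard and experimental treatment". On that footing the section's sample size statement is "N=26 patients are required to be 80% sure". Success is defined by the position of a confidence bound: "the lower limit of a one-sided 97.5% confidence interval will be above the non-inferiority limit of –d".

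The next paragraph says the results will not be normally distributed. For that reason "a Mann-Whitney U test will be used to compare the gains in KM" between the two groups at 6 and at 12 months. It does not say how the test relates to -d. Neither this section nor the objectives names a primary time point.

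Under Study population the recruitment target is given as "A total of 30 patients seeking treatment". The plan states no attrition rate, allocation ratio or outcome distribution.

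**The concern.** The sample size is justified by where a confidence limit for a difference falls. The analysis then named is a rank test, with no confidence limit and no margin. The 80% may therefore describe a calculation that the trial will not carry out.

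Two things are at stake. First, a report that quotes 80% power at 26 would quote a figure that holds neither for an ordinary small-sample interval for means nor, as far as the plan shows, for the rank analysis. Second, 30 recruits against 26 required looks like room for four losses over 12 months. Whether that room exists depends on which analysis is used.

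**Working it through.** **Inputs (Statistical Analysis section).** SD 0.9 mm; margin d = 1 mm; true difference 0; one-sided alpha 0.025; target power 80%. Recruitment of 30 is from Study population. Allocation of 1:1 is my assumption.

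**1. Reproducing the plan's figure.** Known-SD normal approximation for two means:

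n per arm = 2 × 0.9² × (1.960 + 0.842)² / 1² = 1.62 × 7.85 = 12.7, rounded up to 13, so N = 26.

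Power at 13 per arm: the standard error is 0.9 × √(2/13) = 0.353, and 1/0.353 = 2.833. Φ(2.833 − 1.960) = Φ(0.873) = 80.9%. The plan's N is reproduced.

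**2. Same comparison with the SD estimated.** The interval then uses the t distribution with 2n − 2 degrees of freedom. Power is the probability that a noncentral t variable, with noncentrality 1/(0.9 × √(2/n)), exceeds the 97.5% t quantile.

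| Analysed (per arm) | Known SD | t-based |
|---|---|---|
| 26 (13) | 80.9% | 77.6% |
| 28 (14) | 83.6% | 80.8% |
| 30 (15) | 86.1% | 83.6% |

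So 28 evaluable patients are needed to reach 80%. Non-normality does not rescue 26: simulated t-based power stays at about 77% to 79% across the shapes in step 3.

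**3. The named rank test.** Taken literally, an unshifted Mann-Whitney test asks whether the groups differ. If there is no true difference, it is significant only at about its alpha level, and a non-significant result does not establish non-inferiority. The 80% cannot refer to that test.

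The most favourable reading shifts one arm by 1 mm and tests at one-sided 0.025. I simulated this with exact critical values, 100,000 replicates per case and SD 0.9 throughout. The shapes are assumptions.

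| Shape of gains | 26 analysed | 30 analysed |
|---|---|---|
| Uniform | 68.6% | 75.7% |
| Normal | 73.4% | 80.7% |
| Gamma (shape 4) | 79.1% | 85.3% |
| t, 5 df | 81.5% | 87.4% |
| Laplace | 82.7% | 88.5% |
| Lognormal (sigma 0.5) | 85.8% | 91.0% |
| Exponential | 88.1% | 92.5% |

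A repeat for normal gains at 30 gave 80.4%, so about 80% is the right precision. If normal gains are rounded to whole millimetres (also an assumption), power is about 71% to 72% at 26 and 77% to 78% at 30.

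**4. Room for losses from 30.** For the t-based interval, 28 remaining gives 80.8%. With 27 (14 and 13 per arm) the noncentrality is 1/(0.9 × √(1/14 + 1/13)) = 2.885 on 25 degrees of freedom, and power is 79.2%. Two losses are tolerable. For the margin-shifted rank test with normal gains, power is about 80% at 30, 79% at 29 and 78% at 28. No loss is tolerable.

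**The case against.** The strongest reply is that the plan expects non-normal gains, and under several such shapes the margin-shifted rank test exceeds 80% at 26. A reader might infer from the normal-data figure that the planned analysis simply has 73% power. The documents do not support that. The figure needs normal gains, which the plan rejects, and a margin shift, which the plan does not state. This part of the reply stands: a shortfall for the rank test is not established. What remains is that no power was computed for that test and its direction relative to 80% is unknown.

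A second reply is that the trial recruits 30, not 26. A reader might infer that it is underpowered at planned enrolment. It is not on the plan's own inputs if everyone is analysed: the t-based interval gives 83.6%, and the rank version about 80% for normal gains. This also stands. The problem is the claim attached to 26, together with the absence of any stated allowance for loss. The documents do not describe the extra four patients as such an allowance.

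Third, because gains are compared at 6 and 12 months, a reader might infer that both must succeed and that power is lower still. No such rule is written. If one were adopted, rank-based power at 26 with normal gains would be about 60% to 67% for an assumed correlation of 0.5 to 0.9. That is a conditional note and not a defect in the stated figure.

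**Conclusion.** The point holds in limited form. N=26 is arithmetically correct for a known-SD normal approximation, but that is not an analysis the trial can run. For a mean-difference interval with the SD estimated, power at 26 is 77.6%, about 2 percentage points below the stated 80%, and 28 evaluable patients are needed. This rests only on the plan's inputs and 1:1 allocation.

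For the named Mann-Whitney test, the plan gives neither a power figure nor a link to -1 mm. Supplying the margin shift, power ranges from about 69% to 88% at 26 and from 75.7% to 92.5% at 30, depending on a shape the plan does not give. The error is modest for the t-based interval and of undetermined sign for the rank test. It is worth correcting because the correction is cheap.

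**What to change.** Amend the Statistical Analysis section as follows.

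- State a margin-based primary analysis: either a t-based interval, or a Hodges-Lehmann interval obtained by inverting the Mann-Whitney test. In either case, compare the one-sided 97.5% lower limit for CTG plus laser gingivoplasty minus FGG with -1 mm.
- Restate power for the analysis chosen. t-based: 78% at 26, 81% at 28, 84% at 30. Rank-based: about 73% at 26 and 80% at 30 if gains are normal, with the range by assumed shape shown beside it.
- State how many of the 30 recruits can be lost before power falls below 80%: two for the t-based interval; none for the rank-based interval if gains are normal.
- Name 6 or 12 months as the primary time point to which the power statement applies.

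This is a wording change with no added enrolment. The cost is that the stated power becomes slightly less favourable.

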The surgical sites will be examined at 1 and 2 weeks after surgical visits and loose sutures will be removed. Exams will then be scheduled at 1, 3, 6, and 12 months post-op. For participants in Group 2 (CTG), a CO2 Laser gingivoplasty will be performed at 1-month follow-up taking in account the CTG dimensions and flap thickness at time of grafting in order to expose underlying CTG to induce formation of keratinized epithelium.

The clinical parameters and the respective timing of the measurements will be evaluated for all patients as indicated in Table 2.

Table 2. Clinical parameters and their respective timing of measurement

Clinical parameters	Timing of measurements
Probing Depth (PD) using UNC periodontal probe (in mm) using a custom acrylic	Screening, Surgery (Pre-surgical),
stent	at 3, 6 and 12 months post-op
Width of Keratinized Mucosa (KM) using UNC periodontal probe (in mm) using a	Screening, Surgery (Pre-surgical),
custom acrylic stent	at 3, 6 and 12 months post-op
Width of attached mucosa (AM) will be calculated by subtracting PD from KM	Screening, Surgery (Pre-surgical),
An) Sen/	at 3, 6 and 12 months post-op
Tissue Thickness (TT1 and TT2) of peri-implant buccal mucosa will be measured	Screening, Surgery (Pre-surgical),
during the surgical visit by horizontal transmucosal probing using an endodontic	at 3, 6 and 12 months post-op
reamer after local infiltration of anesthetic prior to surgical site preparation. TT1	
and TT2 will be measured at 2 mm and 5 mm from the mucosal margin,	
respectively, using a custom acrylic stent	
Plaque Index (PI) according to Silness & Löe (1964) ¹⁷	Screening, Surgery (Pre-surgical),
	at 1, 3, 6 and 12 months post-op

Esthetic Outcomes

A newly developed peri-implant esthetic scale (PIES) will be used by a second trained calibrated examiner to objectively evaluate standardized clinical photographs taken at 6-months and 1-year after soft tissue grafting. Transparency, blending, recession/level of soft-tissue margin, gingival color, and muco-gingival junction alignment will be recorded and compared.

Patient-centered outcomes

A customized visual analog scale (VAS) will be completed by patients at 1 week (both groups) and 5 weeks post-op (CTG+LG group only) using a scale of 1 through 10: 1-having the least pain/bleeding/swelling/satisfaction/impact on daily activity and 10-having the most pain/bleeding/swelling/satisfaction/ impact on daily activity.

Statistical Analysis

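### The plan sets a non-inferiority criterion (one-sided 97.5% lower limit above -1 mm), but its only planned analysis, a Mann-Whitney test, is not tied to that criterion

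*Combined protocol and SAP*

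**What the plan says.** The first paragraph of Statistical Analysis declares the design: "The non-inferiority design of the current study operates on an assumed standard deviation (SD) of .9", with a margin d of 1 mm. The criterion appears only inside the sample-size sentence. If the treatments truly do not differ, 26 patients give 80% assurance that the "lower limit of a one-sided 97.5% confidence interval will be above the non-inferiority limit" of -d.

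The second paragraph begins "Since the results will not follow a normal distribution" and gives the only planned analysis: "a Mann-Whitney U test will be used to compare the gains in KM around dental implants between the control (FGG) and test group", "at 6 months and 12 months post-operatively". It does not mention the margin, a confidence interval, a one- or two-sided level, or what result counts as success.

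Section 1 (Objectives/Specific Aims) labels the following as the null hypothesis: "there will be a statistically significant difference between FGG and CTG + gingivoplasty when used to increase WKM around dental implants", at both 6 and 12 months. The Study population paragraph sets recruitment: "A total of 30 patients seeking treatment". The allocation ratio is not stated.

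**The concern.** A non-inferiority conclusion needs a test or interval set against the margin. A standard Mann-Whitney test is set against zero. The criterion is on one scale, the analysis answers another question, and no sentence connects them. The analyst would have to choose the connection, possibly after seeing the data.

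The stated null does not help. A non-inferiority null does posit a difference, but one with a direction and a size: CTG+LG worse than FGG by 1 mm or more. The plan's null has neither. As the null of a test of difference, it is reversed. Read literally, it makes absence of a significant difference look like the result to be shown, and no sentence in the plan excludes that reading.

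**Working it through.** **Inputs.** From Statistical Analysis: SD 0.9 mm, d = 1 mm, true difference 0, one-sided 2.5%, 80% power, N=26. From Study population: 30 recruited. Assumed: 1:1 allocation, normal gains unless stated, and a two-sided 5% level for the unshifted test. Differences are CTG+LG minus FGG.

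**1. The plan's own figure.** n per arm = 2·SD²·(z₀.₉₇₅ + z₀.₈)²/d² = 2 × 0.81 × (1.960 + 0.842)² / 1² = 12.7. This rounds up to 13 per arm, 26 in total. N=26 reproduces.

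**2. Why one p-value can go with either answer.** As an illustration on means, with 13 per arm and an observed SD of 0.9, the 95% half-width is t₀.₉₇₅,₂₄ × 0.9 × √(2/13) = 0.729 mm. The difference is non-significant whenever it lies within ±0.729. The lower limit clears -1 mm only when the difference exceeds -1 + 0.729 = -0.271. An observed difference between -0.729 and -0.271 is therefore non-significant and also fails the criterion.

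**3. The same point for the rank test.** Simulation with 13 per arm, normal gains and a tie-corrected Mann-Whitney test. Here, meeting the limit means passing the one-sided 2.5% Mann-Whitney test after 1 mm is added to each CTG+LG gain.

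| True difference | Unshifted test non-significant | Of those, meet the -1 mm limit | Non-significant but fail (product) |
|---|---|---|---|
| 0 mm | 95.6% | 74.4% | 0.956 × 0.256 = 24% |
| -0.5 mm | 75.3% | 32.3% | 0.753 × 0.677 = 51% |
| -1 mm | 26.6% | 8.4% | 0.266 × 0.916 = 24% |

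This table does not depend on how anyone would interpret the p-value. Over the other shapes tried (gamma, t, whole-millimetre values), the 32% at -0.5 mm ranges from 30% to 50%.

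**4. Conditional consequence.** Suppose non-significance were read as non-inferiority. A true 1 mm deficit would then pass in about 27% of trials at N=26 and 20% at N=30 with normal gains, against the intended 2.5%. Over the shapes tried, including a flat one, the ranges are about 15-31% and 10-24%.

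**5. Error rate of a margin-linked rank rule.** If the two arms' gains differ only by a shift, a true -1 mm passes in about 2.0-2.5% of trials. If spread or skew differs, a true mean difference of -1 mm gives other rates:
- gamma shape 2 gains, SD 0.5 for CTG+LG and 1.17 for FGG: 9.4% at 13 per arm, 10.2% at 15;
- those SDs swapped: 0.7%;
- opposite skews: 8.3%;
- normal CTG+LG gains, gamma FGG gains: 4.2%;
- normal gains with unequal SDs: about 2.8%.

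**6. Power of the rank rule at no true difference.** With normal gains it is 74% at N=26 and 80% at N=30. A t-based limit on means gives 78% and 84%. Over all shapes tried, the rank rule ranges from about 69% to 85% and from 76% to 90%.

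**7. Two visits (normal approximation, 13 per arm).** Success at either visit gives an overall error of 1 - 0.975² = 4.9% if the visits are uncorrelated, falling to 3.5% at correlation 0.9. Requiring both gives power of 0.809² = 65% if uncorrelated, rising to 76% at correlation 0.9. The correlations are assumptions.

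**The case against.** The strongest reply is that the decision rule is already there: the sizing sentence defines success by a limit against -d, and a fair reader would apply it. That is partly right. The intention is visible, and it counts against assuming that a non-significant p-value would be taken as success. But no interval method is planned, and the sizing formula is a normal approximation for means, while the next paragraph expects non-normal results. The intention is not carried into an analysis that can be run.

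It can also be said that rank methods suit non-inferiority. They do, through a Hodges-Lehmann interval or a margin shift. The fault is the missing link, not the choice of Mann-Whitney.

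The null may be a drafting slip, and naming 6 and 12 months can be read as requiring both. Both replies are reasonable. The lack of a deciding visit is a secondary gap.

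Three stronger readings are tempting, and the documents do not support them:
- That the trial carries a 27% false-positive risk. This needs a reading of non-significance that the plan nowhere states.
- That the sample size is wrong. It reproduces under its own assumptions.
- That 30 recruits contradict N=26. The surplus of four can be read as an allowance for loss, although the plan does not say so.

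**Conclusion.** The concern holds and should be fixed before analysis. The plan states a non-inferiority criterion, but the analysis it names does not produce a decision on that criterion, and the stated null has no margin or direction. The size that needs no assumption about interpretation is this: at a true -0.5 mm, about 75% of trials are non-significant, and about two thirds of those do not meet the limit. This rests on SD 0.9, 13 per arm and normal gains. The 27% and 20% figures are conditional and should be cited only as the reason to exclude that reading. A margin-linked rank rule holds its 2.5% error only if the arms differ by a shift. That is not assured here, because the two procedures differ in flap design, graft coverage and the later laser step.

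**What to change.** In Objectives and Statistical Analysis:

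- State H0: location shift in KM gain (CTG+LG minus FGG) ≤ -1 mm, against H1: > -1 mm.
- Specify one decision rule. Either the one-sided 97.5% Hodges-Lehmann lower limit (by Mann-Whitney inversion) is above -1 mm, which keeps the criterion the section already words, or its counterpart, a one-sided 2.5% tie-corrected Mann-Whitney test after adding 1 mm to each CTG+LG gain.
- State that a non-significant test of difference will not be read as non-inferiority.
- State that the 2.5% error rate assumes the arms' gains differ only by a shift. Add a mean-difference interval allowing unequal variances as a sensitivity analysis.
- Secondary: say whether 6 months, 12 months or both decides.
- If a test of difference is in fact intended, restate the null as no difference and re-justify N for that test.

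Cost: no new data, visits or patients, but the change is not free. The stated 80% at N=26 belongs to a normal-approximation limit on means. With normal gains the rank rule has about 74% power at 26 evaluable patients and about 80% at 30, so 80% needs every recruit to be evaluable. Requiring both visits lowers power further. Note this beside the N=26 statement, as dependent on the unknown distribution of gains.

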Patients:	Systemic conditions contraindicating oral surgical procedures or adversely affecting wound healing Crestal bone loss extending apical to first implant thread Presence of peri-implantitis, acute infection and/or suppuration at the implant placement site(s)
One or more adjacent dental implants having WKM <2mm around the buccal aspect. [if there are multiple affected adjacent implants, they will all be treated but only 1 implant with the least WKM will be included in the analysis]	Presence of soft tissue recession exposing threads at implant site
Timing of intervention: Implants with healing abutments awaiting restoration or after delivery of temporary/permanent restoration	Absence of buccal plate of bone
Periodontally healthy neighboring teeth, healthy implants or edentulous ridge on either side of the involved site (s)	Previous soft tissue grafting at the implant site(s)

Surgical Visit

Group 1: Under local anesthesia, the implant site (s) will be prepared with a trapezoidal split-thickness flap on buccal aspect leaving a thin periosteum as recipient bed. Mesio-distal and apico-coronal dimensions will be measured at recipient site and a FGG with equal dimensions and uniform thickness will be harvested from the patient's palate. Exact FGG dimensions will be measured with a UNC-15 periodontal probe and its thickness will be measured using a caliper prior to placement at recipient site. FGG will be secured in position with multiple suture techniques. KM will then be measured immediately after FGG is secured. Donor site will be treated with wet gauze compression or placement of hemostatic agent if needed, and a prepared acrylic palatal stent will be delivered.

Group 2: A similar procedure will be performed with the following differences. The flap at the recipient site will be full-thickness in design. CTG harvesting from the patient's palate will be completed using a single incision or trap door technique leaving a minimal wound. After CTG is secured with sutures, the full-thickness flap will be repositioned to achieve complete CTG coverage.

Figure 1 illustrates the treatment of two implants with lack of KM using FGG.

[figure not shown]

Fig. 1. Implants with KM=0 (left)-note inflamed mucosa around implants. Creation of an adequate zone of KM 3 months following treatment with FGG (right)-note increase in tissue thickness and absence of inflammation signs

Follow-up Visits and Clinical Outcomes

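### KM gains are compared without adjusting for baseline KM, a cheap precision improvement of uncertain size; which pre-treatment reading is baseline is also not stated

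*Combined protocol and SAP*

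**What the plan says.** The one KM comparison in the Statistical Analysis section is that "a Mann-Whitney U test will be used to compare the gains in KM around dental implants between the control (FGG) and test group", "at 6 months and 12 months post-operatively". The reason given for a rank test is "Since the results will not follow a normal distribution". The sample size has a different target, namely that "the lower limit of a one-sided 97.5% confidence interval will be above the non-inferiority limit" of minus 1 mm. No covariate, stratum or adjusted analysis appears anywhere in the document.

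The KM row of Table 2 lists two pre-treatment readings, "Screening, Surgery (Pre-surgical"), before the follow-up readings. Gain is not defined, and neither reading is called baseline. Table 1 limits entry to "One or more adjacent dental implants having WKM <2mm around the buccal aspect", and the Fig. 1 caption shows that a site can start at zero: "Implants with KM=0 (left)-note inflamed mucosa around implants". The Randomization section states: "Randomization will take place on the day of surgery via sealed envelopes". It does not say whether the pre-surgical reading comes before or after the envelope is opened.

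**The concern.** A gain uses baseline with a fixed weight of 1. If follow-up KM depends on starting KM less than one-for-one, subtraction adds chance baseline differences to the outcome instead of removing them. That is plausible when a graft creates new keratinised tissue. Adjustment lets the data set the weight. With 26 patients required and 30 recruited, precision is scarce, and the covariate is already being measured.

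There is a smaller, related point. With two candidate baselines and no rule, two analysts could compute different gains from the same patients, and the choice could be made after the data are seen.

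**Working it through.** **Inputs from the document.** SD 0.9 mm, margin 1 mm, true difference 0, one-sided 2.5%, power 80%, N=26, recruitment 30, entry KM below 2 mm.

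**Assumptions.** Allocation is 1:1. The SD of 0.9 is that of the gain (the document does not say). Baseline SD is 0.2 to 0.58 mm, where 0.58 is an even spread over 0 to 2 mm (2/√12). Baseline-to-follow-up correlation ρ is 0 to 0.4. Residuals are normal or skewed (exponential). The margin enters by adding 1 mm to CTG+LG before ranking, because the plan does not say how it enters the Mann-Whitney test.

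**The plan's own figure.** 2 × (0.9 × (1.960 + 0.842) / 1)² = 12.72, so 13 per arm and N=26. This matches. Power at 13 per arm is 81% by the normal approximation and 78% by the t-test.

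**Validity.** In simulations of 13 per arm with no true difference, the mean arm difference in gain was -0.001 to 0.003 mm. The two-sided Mann-Whitney error was 4.1% to 4.8% against a nominal 5%. Leaving out the adjustment therefore causes no bias and no inflation of error. With baseline SD 0.5 mm, chance imbalance between arms has SD 0.5 × √(2/13) = 0.20 mm. It moves the gain difference by (b − 1) times the imbalance, where b is the slope of follow-up KM on baseline. This is noise across trials, not a systematic error.

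**What adjustment can remove.** Solve SDy² + SDb² − 2ρ·SDy·SDb = 0.81 for the follow-up SD (SDy). The residual SD is SDy·√(1 − ρ²). For SDb 0.58 and ρ = 0: SDy² = 0.81 − 0.336 = 0.474, so the residual SD is 0.688 and the variance falls by 1 − 0.474/0.81 = 42%. For SDb 0.4 and ρ = 0.4: SDy = 0.982 and b = 0.4 × 0.982/0.4 = 0.98. Subtraction is then already near optimal and nothing is removed.

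**Power at 13 per arm.** Simulated, exact critical U = 124, attained one-sided level 2.2%. Each pair is planned test / adjusted rank test.

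| SDb | ρ | Variance fall | Normal | Skewed |
|---|---|---|---|---|
| 0.58 | 0 | 42% | 73% / 91% | 78% / 95% |
| 0.58 | 0.2 | 21% | 73% / 81% | 83% / 91% |
| 0.58 | 0.4 | 5% | 73% / 73% | 88% / 87% |
| 0.4 | 0 | 20% | 73% / 80% | 84% / 91% |
| 0.4 | 0.2 | 6% | 74% / 74% | 87% / 87% |
| 0.4 | 0.4 | 0% | 73% / 71% | 88% / 85% |
| 0.2 | 0 to 0.4 | 0% to 5% | 73–74% / 71–74% | 88% / 86–87% |

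Repeat runs differ by up to about a point; the 85% to 96% quoted for the adjusted test with skewed residuals allows for that. At 15 per arm with normal residuals and SDb 0.4 to 0.58, the planned test has about 80% and the adjusted test 78% to 95%. One-sided error of the adjusted test at a true difference of -1 mm is 1.9% to 2.4%. An interval taken from residuals that were not shifted first has error 2.7% to 3.7%, so the shift must come before the regression.

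**Unnamed baseline.** Suppose each reading has independent error with SD e. The two arm differences then differ with SD e·√2·√(2/13), which is 0.17 mm at e = 0.3 and 0.28 mm at e = 0.5. Flooring readings at zero reduces this to 0.13 to 0.25 mm. The table gives how often the verdict changes with the reading used, at 13 per arm with truly equal arms.

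| Assumed e | Ordinary two-sided test | Test shifted by 1 mm |
|---|---|---|
| 0.1 to 0.2 mm | about 1% to 3% | about 5% to 16% |
| 0.3 to 0.5 mm | 3% to 7% | 7% to 22% |

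**The case against.** The strongest reply is that subtraction is a legitimate choice, the planned test is valid, and the benefit of adjustment may be nil or slightly negative. All of that stands, and it is why this is a suggestion and not a defect. What remains is the asymmetry: a loss of at most 2 to 3 points against a possible gain of about 18, from data already collected.

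A reader might infer that the unadjusted comparison is biased. The documents do not support that. Selecting sites with low KM affects both arms alike, and randomisation protects the comparison. The one condition is that the baseline is read before allocation is known, which the Randomization section leaves open.

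A reader might also infer that the unnamed baseline would overturn the non-inferiority verdict in up to about one trial in five. That figure needs a shifted test that the plan does not contain and reading error at the top of the assumed range. The protocol uses one calibrated examiner and a custom stent, which argue for smaller error. For the ordinary test the range is roughly 1% to 7%.

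Finally, the largest gains need a wide baseline spread and a correlation near zero. If most sites start near 0 mm, there is no gain.

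**Conclusion.** The point holds as a low-cost improvement, at the level of something to consider. The planned test ignores usable baseline information, but it is valid, and it is unbiased on the timing condition above. Across the assumed inputs, adjustment changes power at 13 per arm by between a loss of 2 to 3 points and a gain of about 18. Where in that range this trial lies cannot be settled from the documents, because they give neither the baseline SD nor the correlation. The undefined baseline is a real but secondary gap in prespecification, and its effect depends on a reading error that is likewise not given. That the Mann-Whitney test supplies no confidence limit against -1 mm is a separate issue and should be raised separately.

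**What to change.** Define KM gain as follow-up KM minus the pre-surgical KM, read on the day of surgery before the envelope is opened, with screening KM as the fallback if that reading is missing.

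Before any follow-up KM is examined, prespecify the CTG+LG minus FGG difference at 6 and 12 months adjusted for that baseline. A rank-based method respects the plan's expectation of non-normal data: add 1 mm to follow-up KM in CTG+LG, regress follow-up KM on baseline ignoring arm, and apply the one-sided 2.5% Mann-Whitney test to the residuals. State a rule for ties, since probe readings will often coincide. Keep the unadjusted Mann-Whitney test on gains as a supporting analysis.

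Naming the baseline costs a sentence and a small conduct rule about the order of events on the day of surgery. Adjustment costs one degree of freedom, some custom code, and up to about 3 points of power at 13 per arm (about 2 at 15) if subtraction is already near optimal. No extra visit or measurement is needed.
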